7.3 Loss of Participants to Follow-Up

A participant will be considered lost to follow-up if he or she is unable to be contacted by the study site. The following actions must be taken if a participant cannot be contacted at Day 14 or Day 28:

- The site must attempt to contact the participant and counsel the participant on the importance of maintaining the assigned schedule and ascertain whether or not the participant wishes to and/or should continue in the study.
- In cases in which the participant is deemed lost to follow-up, the Investigator or designee must make every effort to regain contact with the participant (where possible, three telephone calls and, if necessary, a certified letter to the participant's last known mailing address or local equivalent methods). These contact attempts should be documented in the participant's medical record/CRF.
- Should the participant continue to be unreachable, he/she will be considered to have withdrawn from the study.

8 Study Assessments and Procedures

Study procedures and their timing are summarized in the SoA ([Table 1-1](#)). Protocol waivers or exemptions are not allowed.

Immediate safety concerns should be discussed with the Sponsor immediately upon occurrence or awareness to determine if the participant should continue or discontinue study intervention.

Adherence to the study design requirements, including those specified in the SoA, is essential and required for study conduct.

All screening evaluations must be completed and reviewed to confirm that potential participants meet all eligibility criteria. The Investigator will maintain a screening log to record details of all participants screened and to confirm eligibility or record reasons for screening failure, as applicable.

Procedures conducted as part of the participant's routine clinical management (e.g., blood count) and obtained before signing of the ICF may be utilized for screening or baseline purposes provided the procedures met the protocol-specified criteria and were performed within the time frame defined in the SoA ([Table 1-1](#)).

The maximum amount of blood collected from each participant over the duration of the study, including any extra assessments that may be required, will not exceed 20 mL.

Repeat or unscheduled samples may be taken for safety reasons or for technical issues with the samples.

Informed Consent

Informed consent must be documented according to [Appendix 1, Section 10.1.3](#).

Eligibility Criteria

All inclusion and exclusion criteria will be reviewed by the Investigator or designee to ensure that the participant qualifies for the study.

Participant Identification Card

All participants will be given a participant identification card identifying them as participants in a research study. The card will contain study site contact information (including direct telephone numbers) to be used in the event of an emergency. The Investigator or qualified designee will provide the participant with a participant identification card immediately after the participant provides written informed consent. At the time of intervention allocation/randomization, site personnel will add the intervention/randomization number to the participant identification card.

Medical History

A medical history will be obtained by the Investigator or qualified designee. The medical history will collect all active conditions and any condition diagnosed that the Investigator considers to be clinically relevant. Details regarding the disease for which the participant has enrolled in this study will be recorded separately and not listed as medical history.

Prior and Concomitant Medications Review

The Investigator or qualified designee will review prior medication use and record prior medications taken by the participant within 3 months prior to screening. This should include a history of hypertension medication, in particular angiotensin-converting enzyme inhibitors and angiotensin receptor blockers.

The Investigator or qualified designee will record medication, if any, taken by the participant during the study through the last assessment. Concomitant medications will be recorded on an ongoing basis during the study (or longer if related to an SAE).

8.1 Efficacy Assessments

8.1.1 Modified WHO Ordinal Scale

A modified WHO ordinal scale will be used for consistency with the recent study of lopinavir-ritonavir in adults hospitalized with severe COVID-19 (Cao et al, 2020), to record the participant's status at the time of assessment. The modified WHO ordinal scale includes the following levels:

1. Not hospitalized, no limitations on activities;
2. Not hospitalized, limitation on activities;
3. Hospitalized, not requiring supplemental oxygen;
4. Hospitalized, requiring supplemental oxygen;
5. Hospitalized, on non-invasive ventilation or high-flow oxygen devices;
6. Hospitalized, on invasive mechanical ventilation or extra corporeal membrane oxygenation (ECMO);
7. Death.

8.1.2 Pulse Oximetry

Pulse oximetry measurements will be performed to evaluate SpO₂ as outlined in the SoA (Table 1-1) and in accordance with the site standard operating procedures, on a medical-grade medical device. Measurements will be taken with a probe on fingertip or earlobe and recorded as percent oxygenated hemoglobin. Supplemental oxygen used at the time of assessment and method of oxygen delivery will be collected and documented along with the SpO₂.

Prior to administration of study intervention, supplemental oxygen will be held for at least a minute and SpO₂ checked in order to ensure participant may safely receive the study intervention. For safety reasons, since due to the current pandemic it cannot be guaranteed that study intervention will be consistently administered under direct medical supervision, the study Investigators should provide study personnel who are able to monitor the participant and their SpO₂ and ensure that should it decline to a threshold, this would trigger immediate discontinuation. By default, unless overruled by the study Investigator, this SpO₂ threshold is set to 89%. This threshold should be entered into the saturation monitoring device to trigger an alarm during nebulization.

FiO₂ will be measured per site standard practice and recorded in the eCRF. The device used to administer oxygen should also be recorded.

8.1.3 National Early Warning Score (NEWS) 2

The NEWS 2 will be measured prior to study intervention in the morning according to the SoA in [Table 1-1](#).

The NEWS is based on a simple aggregate scoring system in which a score is allocated to physiological measurements, already recorded in routine practice, when patients present to, or are being monitored in hospital ([RCP, 2012](#)). Six simple physiological parameters form the basis of the scoring system:

1. Respiration rate
2. Oxygen saturation
3. Systolic blood pressure
4. Pulse rate
5. Level of consciousness or new confusion*
6. Temperature

**The patient has new-onset confusion, disorientation and/or agitation, where previously their mental state was normal – this may be subtle. The patient may respond to questions coherently, but there is some confusion, disorientation and/or agitation. This would score 3 or 4 on the Glasgow Coma Scale (rather than the normal 5 for verbal response), and scores 3 on the NEWS system.*

A score is allocated to each parameter as they are measured, with the magnitude of the score reflecting how extremely the parameter varies from the norm (zero for ‘normal’; maximum score 3). The score is then aggregated. The score is increased by 2 points for people requiring supplemental oxygen to maintain their recommended oxygen saturation. This is a pragmatic approach, with a key emphasis on system-wide standardization and the use of physiological parameters that are already routinely measured in National Health Service (NHS) hospitals and in prehospital care, recorded on a standardized clinical chart – the NEWS 2 chart (Refer to [Appendix 2: The NEWS 2 Scoring System](#)).

Reproduced from: Royal College of Physicians. National Early Warning Score (NEWS) 2: Standardising the assessment of acute-illness severity in the NHS. Updated report of a working party. London: RCP, 2017 ([RCP, 2017](#)).

8.2 Safety Assessments

Planned time points for all safety assessments are provided in the SoA ([Table 1-1](#)).

8.2.1 Physical Examinations

A complete physical examination will include, at a minimum, assessments of the head/ear/eyes/nose/throat, cardiovascular, respiratory, gastrointestinal, lymphatic, skin and neurological systems. Height (screening only) and weight will also be measured and recorded.

A brief physical examination will include, at a minimum, assessments of the skin, lungs, cardiovascular system, and abdomen (liver and spleen).

8.2.2 Vital Signs

Vital signs to be collected as outlined in the SoA ([Table 1-1](#)) and include body temperature, heart rate, blood pressure, and respiratory rate.

Body temperature will be assessed per the local practice (temporal or otic are preferred sites), and site will be recorded. Pulse rate, respiratory rate, and blood pressure will also be assessed per site SOC. Where possible the same methods should be used throughout the study for an individual participant.

Blood pressure and pulse measurements should be preceded by at least 5 minutes of rest for the participant in a quiet setting without distractions (e.g., television, cell phones). During study intervention administration, an alarm threshold should be set for heart rate at 120 beats/min (or as indicated by the Investigator), as outlined in the SoA ([Table 1-1](#)).

Vital signs (to be taken before blood collection for laboratory tests) will consist of one pulse and one blood pressure measurement (after the participant has been sitting for 5 minutes).

8.2.3 Electrocardiograms

Single 12-lead ECG will be obtained as outlined in the SoA ([Table 1-1](#)) using an ECG machine that automatically calculates the heart rate and measures PR, QRS, QT, and QTcF intervals for local reading.

8.2.4 Clinical Safety Laboratory Assessments

Refer to [Appendix 3](#) for the list of clinical laboratory tests to be performed and to the SoA ([Table 1-1](#)) for the timing and frequency.

The Investigator must review the laboratory report, document this review, and record any clinically relevant changes occurring during the study in the AE section of the CRF. The laboratory reports must be filed with the source documents. Clinically relevant abnormal laboratory findings are those which are not associated with the underlying disease, unless judged by the Investigator to be more severe than expected for the participant's condition.

All laboratory tests with values considered clinically abnormal during participation in the study or within 4 days after the last dose of study intervention should be repeated until the values return to normal or baseline or are no longer considered clinically significant by the Investigator or Medical Monitor.

- If such values do not return to normal/baseline within a period of time judged reasonable by the Investigator, the etiology should be identified, where possible, and the Sponsor notified.
- All protocol-required laboratory assessments, as defined in [Appendix 3](#), must be conducted in accordance with the laboratory manual and the SoA ([Table 1-1](#)).
- If laboratory values from laboratory assessments not specified in the protocol and performed at the institution's local laboratory result in the need for a change in participant management or are considered clinically relevant by the Investigator (e.g., are considered to be an SAE or an AE or require dose modification), then the results must be recorded in the CRF.

8.3 Adverse Events and Serious Adverse Events

The definitions of AEs and SAEs can be found in [Appendix 4](#).

Table 8-1 summarizes the categories of AEs.

Table 8-1 Categories of Adverse Event

	Non-device related	Device- or procedure-related
Non-Serious	AE (includes all categories)	ADE
Serious	SAE (includes all categories that are serious)	SADE
		Anticipated Unanticipated
		ASADE USADE

Abbreviations: ADE=adverse device effect; AE=adverse event; ASADE=anticipated serious adverse device effect; SADE=serious adverse device effect; SAE=serious adverse event; USADE=unanticipated serious adverse device effect

The definitions of AEs and SAEs (including adverse device effects [ADEs], serious ADEs [SADEs], and unanticipated SADEs [USADEs]), can be found in [Appendix 5](#). Device deficiencies are covered in [Section 8.3.8](#).

Adverse events will be reported by the participant (or, when appropriate, by a caregiver, surrogate, or the participant's legally authorized representative).

The Investigator and any qualified designees are responsible for detecting, documenting, and reporting events that meet the definition of an AE or SAE and remain responsible for following up AE that are serious, considered related to the study intervention or the study, or that caused the participant to discontinue the study intervention (see [Section 7](#)).

8.3.1 Time Period and Frequency for Collecting AE and SAE Information

All AEs and SAEs will be collected from randomization until the last follow-up visit at the time points specified in the SoA ([Table 1-1](#)).

Medical occurrences that begin before the start of study intervention but after obtaining informed consent will be recorded on the Medical History/Current Medical Conditions section of the CRF not the AE section.

All SAEs will be recorded and reported to the Sponsor or designee within 24 hours, as indicated in [Appendix 4](#). The Investigator will submit any updated SAE data to the Sponsor within 24 hours of it being available.

Investigators are not obliged to actively seek AEs or SAEs after the conclusion of study participation. However, if the Investigator learns of any SAE, including a death, at any time after a participant has been discharged from the study, and he/she considers the event to be reasonably related to the study intervention or study participation, the Investigator must promptly notify the Sponsor.

8.3.2 Method of Detecting AEs and SAEs

The method of recording, evaluating, and assessing causality of AEs and SAEs and the procedures for completing and transmitting SAE reports are provided in [Appendix 4](#).

Care will be taken not to introduce bias when detecting AEs and/or SAEs. Open-ended and non-leading verbal questioning of the participant is the preferred method to inquire about AE occurrence.

8.3.3 Follow-up of AEs and SAEs

After the initial AE/SAE report, the Investigator is required to proactively follow each participant at subsequent visits/contacts. All SAEs will be followed until resolution, stabilization, until the event is otherwise explained, or the participant is lost to follow-up (as defined in Section 7.3). Further information on follow-up procedures is given in [Appendix 4](#).

8.3.4 Regulatory Reporting Requirements for SAE

Prompt notification (within 24 hours, see [Appendix 4](#)) by the Investigator to the Sponsor of an SAE is essential so that legal obligations and ethical responsibilities towards the safety of participants and the safety of a study intervention under clinical investigation are met.

The Sponsor has a legal responsibility to notify both the local regulatory authority and other regulatory agencies about the safety of a study intervention under clinical investigation. The Sponsor will comply with country-specific regulatory requirements relating to safety reporting to the regulatory authority, Institutional Review Board (IRB)/Independent Ethics Committee (IEC), and Investigators.

For all studies except those utilizing medical devices, Investigator safety reports must be prepared for suspected unexpected serious adverse reactions (SUSARs) according to local regulatory requirements and Sponsor policy and forwarded to Investigators as necessary.

An Investigator who receives an Investigator safety report describing an SAE or other specific safety information (e.g., summary or listing of SAE) from the Sponsor will file it along with the Investigator's Brochure and will notify the IRB/IEC, if appropriate according to local requirements.

8.3.5 Pregnancy (Not Applicable)

Women of childbearing potential and pregnant women are allowed in the study.

8.3.6 Disease-Related Events and/or Disease-Related Outcomes Not Qualifying as AEs or SAEs

The following disease-related events (DREs) are common in participants with COVID-19 and can be serious/life-threatening:

- Fever
- Cough
- Dyspnea*

- Asthenia

** A cough or dyspnea episode related to study intervention administration does not meet the definition of a DRE and should be reported as an AE.*

Because these events are typically associated with the disease under study, they will not be reported as AEs.

NOTE: However, if either of the following conditions applies, then the event must be recorded and reported as an SAE (instead of a DRE):

- The event is, in the Investigator's opinion, of greater intensity, frequency, or duration than expected for the individual participant.

OR

- The Investigator considers that there is a reasonable possibility that the event was related to study intervention.

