	
irritant at the average dose of a positive mannitol test (239.0 ± 185.0 mg, Brannan et al, 2005). While the dose used in this study (54.66 mg) is lower than the average dose for a positive mannitol test, it has not yet been tested in COVID-19 patients and may potentially cause or exacerbate cough or bronchospasm in susceptible individuals in this specific population
	
(such as in asthma) or presence of signs of significant bronchospasm on examination will be excluded from study participation (Exclusion criterion 5)
 
For the first 10 participants treated before the first IDMC safety review (Section 9.6), RESP301 will be administered by intermittent inhalation until the intended dose is delivered (Section 6.1), so that the treatment can be quickly adjusted and rescue bronchodilator initiated if needed (Section 6.5.1)
 
After reviewing safety data, the IDMC will decide whether the intermittent inhalation of RESP301 can be replaced by continuous inhalation.

Study Procedures		
Nebulization	
The delivered dose of RESP301, estimated to be ~40% of the masses listed in Table 6-2, can be affected by patient technique and inspiratory capacity leading
	
Training will be provided to study staff to minimize variation in dose

Potential Risk of Clinical Significance	Summary of Data/Rationale for Risk	Mitigation Strategy
	to inter- and intra-patient variation in actual doses of these ingredients, given the acute nature and high disease burden in this proposed clinical setting	
Other		
Risk of spreading SARS-CoV-2	SARS-CoV-2 is known to be transmissible via respiratory droplets and any interventions that may potentially increase cough or aerosolization of respiratory secretions of an infected patient may increase risk of spread of disease	Proper personal protective equipment including appropriate mask, face shield, gown and gloves should be used at all times. When possible, the site staff should not remain in the room during study intervention administration (providing that continuous O ₂ monitoring can be conducted remotely and study intervention can be administered correctly)

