8.3.6 Disease-Related Events and/or Disease-Related Outcomes Not Qualifying as AEs or SAEs

The following disease-related events (DREs) are common in participants with COVID-19 and can be serious/life-threatening:

- Fever
- Cough*
- Dyspnea*
- Asthenia
- Loss of sense of taste and smell

**A cough or dyspnea episode related to study intervention administration does not meet the definition of a DRE and should be reported as an AE.*

Because these events are typically associated with the disease under study, they will not be reported as AEs.

NOTE: However, if either of the following conditions applies, then the event must be recorded and reported as an SAE (instead of a DRE):

- The event is, in the Investigator's opinion, of greater intensity, frequency, or duration than expected for the individual participant.

OR

- The Investigator considers that there is a reasonable possibility that the event was related to study intervention.

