9.4.5.1 Adverse Events

Adverse Events will be coded using the MedDRA coding dictionary.

The number and percentage of participants with any AE, any related AE, any SAE, any related SAE, any severe AE, and related severe AE as well as the total number of events for each category will be summarized. The number of deaths due to an AE, hospitalization due to an AE, and study discontinuation due to an AE will be summarized.

The number and percentage of participants with an AE, as well as the total number of AEs, will be summarized by SOC and preferred term. This tabulation will be repeated for related AEs, SAEs, related SAEs, severe AEs, and related severe AEs.

All AEs will be provided in patient listings. Patient listings of AEs causing discontinuation of study medication, AEs leading to death, SAEs, related AEs, and severe AEs will be produced.

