10.4.1 Definition of AE

AE Definition

• An AE is any untoward medical occurrence in a patient or clinical study participant, temporally associated with the use of a study intervention, whether or not considered related to the study intervention.• NOTE: An AE can therefore be any unfavorable and unintended sign (including an abnormal laboratory finding), symptom, or disease (new or exacerbated) temporally associated with the use of a study intervention.

Events Meeting the AE Definition

• Any abnormal laboratory test results (hematology, clinical chemistry, or urinalysis) or other safety assessments (e.g., ECG, radiological scans, vital signs measurements), including those that worsen from baseline, considered clinically significant in the medical and scientific judgment of the Investigator (e.g., not related to progression of underlying disease).• Exacerbation of a chronic or intermittent pre-existing condition including either an increase in frequency and/or intensity of the condition.• New conditions detected or diagnosed after study intervention administration even though it may have been present before the start of the study.• Signs, symptoms, or the clinical sequelae of a suspected drug-drug interaction.• Signs, symptoms, or the clinical sequelae of a suspected overdose of either study intervention or a concomitant medication. Overdose per se will not be reported as an AE/SAE unless it is an intentional overdose taken with possible suicidal/self-harming intent. Such overdoses should be reported regardless of sequelae.• "Lack of efficacy" or "failure of expected pharmacological action" per se will not be reported as an AE or SAE. Such instances will be captured in the efficacy assessments. However, the signs, symptoms, and/or clinical sequelae resulting from lack of efficacy will be reported as AE or SAE if they fulfill the definition of an AE or SAE.

Events NOT Meeting the AE Definition

- Any clinically significant abnormal laboratory findings or other abnormal safety assessments which are associated with the underlying disease, unless judged by the Investigator to be more severe than expected for the participant's condition.
- The disease/disorder being studied or expected progression, signs, or symptoms of the disease/disorder being studied, unless more severe than expected for the participant's condition.

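### Section 8.3.6 makes the recording of cough and dyspnea depend on treatment arm, so their AE rates cannot be compared between arms without bias

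*Protocol*

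**What the plan says.** Section 8.3.6 names a set of symptoms, cough and dyspnea among them, as disease-related events (DREs). The default rule is: "Because these events are typically associated with the disease under study, they will not be reported as AEs". There are two ways out of it.

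- **Relatedness.** The footnote reads: "A cough or dyspnea episode related to study intervention administration does not meet the definition of a DRE and should be reported as an AE".
- **Worse than expected.** The NOTE covers an event that is, in the investigator's opinion, "of greater intensity, frequency, or duration than expected for the individual participant".

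For the second route, and again for any event with a reasonable possibility of being related to study intervention, the NOTE says "then the event must be recorded and reported as an SAE (instead of a DRE)". The footnote therefore classes a related cough as an AE and the NOTE classes it as an SAE.

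Section 10.4.1 supports the exemption by excluding from the AE definition "The disease/disorder being studied or expected progression, signs, or symptoms of the disease/disorder being studied", unless more severe than expected.

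On risk, Table 2-1 (section 2.2.1) says the nebulized product "may potentially cause or exacerbate cough or bronchospasm". On analysis, section 9.4.5.1 provides that AEs "will be summarized by SOC and preferred term" (SOC here means system organ class). Section 9.4.5 names no DRE table, the Schedule of Activities has an AE/SAE review but no DRE item, and section 8.3.7 defines no AE of special interest.

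The rule is in Version 1.0 and is kept in Amendment 1 (Version 2.0). The Amendment 2 summary of changes lists no change to 8.3.6; the Version 3.0 text of that section is not in the material available.

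**The concern.** In a randomized trial the control arm supplies the background rate of a symptom that the disease also causes. That works only if the symptom is recorded by the same rule in both arms. Here the rule has a relatedness route that only a nebulized participant can take, and a second route that rests on the opinion of an investigator who knows the allocation.

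Two opposite errors follow. If investigators readily attribute cough to dosing, RESP301 shows an excess of cough AEs even when the drug adds none. If they put it down to COVID-19, a real excess does not reach the AE tables. The reader of those tables could not tell which had happened. The matter is more than formal because cough is a symptom the protocol itself links to the product, Amendment 1 calls the trial first-in-man (section 2.2.3), and intolerable worsening of cough is among its reasons for permanent discontinuation (section 7.1).

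**Working it through.** **Step 1. Which route into AE reporting is open to which arm?**

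| Route in 8.3.6 | RESP301 + standard of care | Standard of care alone |
|---|---|---|
| Related to study intervention | open | closed: nothing is administered |
| Worse than expected, investigator's opinion | open, unblinded | open, unblinded |
| Neither | not an AE | not an AE |

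The capture probability is therefore structurally different by arm.

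**Step 2. Does anything else in the protocol restore the comparison?**

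- Bronchospasm is not on the DRE list, so it is reportable as an AE in both arms. It is a different event from cough or dyspnea.
- Section 9.4.5 tabulates inability to tolerate nebulization and bronchial hyper-responsiveness. Both are defined by nebulization and have no control counterpart.
- Respiratory rate, SpO2 and NEWS 2 are collected in both arms. NEWS 2 (Appendix 2) has no cough or dyspnea item.

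None of these gives a by-arm rate of cough or dyspnea.

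**Step 3. How far could the AE table be moved?** The protocol states no rate of cough or dyspnea and no attribution share, so there is no figure of its own to reproduce. The arm sizes of 200 and 100 come from section 9.2; everything else in this step is assumed.

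Formula: recorded rate = true rate × share of episodes captured.

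*No drug effect.* True incidence 40% in both arms, control capture 10%: 0.40 × 0.10 × 100 = 4/100.

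| RESP301 capture | Recorded RESP301 | Recorded control | Spurious excess | Fisher p (two-sided) |
|---|---|---|---|---|
| 10% | 0.40 × 0.10 × 200 = 8/200 (4%) | 4/100 (4%) | 0 points | 1.0 |
| 25% | 0.40 × 0.25 × 200 = 20/200 (10%) | 4/100 (4%) | 6 points | 0.08 |
| 50% | 0.40 × 0.50 × 200 = 40/200 (20%) | 4/100 (4%) | 16 points | 0.0001 |

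If no control episode were captured (0/100), the last two rows would give p = 0.0003 and p < 0.0001. That is the limiting case, because the worse-than-expected route is open to controls.

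*A true drug effect, little captured.* True incidence 30% on control and 45% on RESP301, with 10% captured in each arm. Recorded: 0.30 × 0.10 = 3% and 0.45 × 0.10 = 4.5%. The 15-point difference shrinks to 1.5 points. Power at two-sided 5% with 100 and 200 participants falls from about 71% (all episodes recorded) to about 8%.

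The distortion can run in either direction, and it is nil when capture is equal and there is no drug effect.

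**The case against.** Exempting common disease symptoms from AE reporting is a deliberate choice that spares sites a heavy burden in a pandemic. Attribution has some structure: Table 7-1 separates acute bronchospasm after inhalation from COVID-19 progression by onset, signs and reversibility. The phrase saying that an event is reported instead of a DRE hints that DREs may be a recorded class, and the SAP, not shown, may tabulate them.

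The burden argument stands, and the fix leaves the exemption in place. Table 7-1 concerns bronchospasm, not cough, and cannot open the relatedness route to controls. The SAP argument reaches only so far: an SAP can tabulate only what has been collected, and no procedure in the protocol requires unattributed cough or dyspnea to be collected.

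Three stronger readings are tempting and are not supported.

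- *A reader might infer that RESP301's main expected harm cannot be compared at all.* Table 2-1 names cough or bronchospasm and lists other risks, such as methemoglobinemia, without ranking them. Bronchospasm remains an AE in both arms, and respiratory rate, SpO2 and NEWS 2 are measured in both.
- *A reader might infer that these symptoms reach no safety table.* Attributed episodes enter the AE or SAE tables, and nebulization intolerance and bronchial hyper-responsiveness are tabulated. Only episodes neither attributed nor judged worse than expected lack a named output.
- *A reader might take the small p-values as the size of the defect.* They depend on assumed incidence and capture shares; equal capture gives no spurious excess.

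**Conclusion.** The point holds in a limited form. By the text of 8.3.6, cough and dyspnea are ascertained differently by arm, so their AE rates cannot be compared without bias, and nothing else in the protocol supplies a both-arm rate. This follows from the wording and needs no numerical assumption.

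The size is unknown. With an assumed 40% incidence in both arms, 10% control capture and 10% to 50% RESP301 capture, the spurious excess runs from 0 to 16 percentage points; with low capture a true excess would be largely hidden. Neither direction can be called more likely from the documents.

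It is a collection-stage weakness worth correcting because correction is cheap, not a failure of the whole safety assessment. It touches neither the primary endpoint nor the sample size. The AE/SAE conflict inside 8.3.6 is a separate inconsistency that adds to uneven classification.

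**What to change.** 1. **Section 8.3.6 and the CRF.** At the AE/SAE review already scheduled in both arms, record new or worse cough and new or worse dyspnea (yes/no, intensity, date) regardless of attribution. Keep the exemption from AE/SAE reporting.
2. **Section 9.4.5.1.** Add one table of the incidence of each symptom by arm, disease-related events and AEs combined, beside the table of attributed AEs.
3. **Section 8.3.6.** Reconcile the footnote with the NOTE, so that a related cough or dyspnea episode has one stated reporting class.

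Cost: two CRF items at an existing review, one more table and a wording correction. The downside is slightly more data entry. No assessment visit or treatment rule changes.
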